3.5.2 Serious adverse events

A serious AE (SAE) is an AE occurring at any time during the study (ie, during run-in, treatment, wash-out or follow-up) that fulfils one or more of the following criteria:

- Results in death
- Is immediately life-threatening
- Requires in-patient hospitalization or prolongation of existing hospitalization
- Results in persistent or significant disability/incapacity or substantial disruption of the ability to conduct normal life functions
- Is a congenital abnormality or birth defect
- Is an important medical event that may jeopardize the patient or may require medical intervention to prevent one of the outcomes listed above

Any SAE occurring before the first dose of IP, or more than 42 days after the last dose of IP, is considered non-TEAE, it will be included in the data listings but will not be included in the summary tables of SAEs.

3.5.3 COPD exacerbations

A COPD exacerbation is defined as a change in the patient's baseline dyspnoea, cough, and/or sputum (increase in volume or change in colour towards purulence) that lasts ≥ 3 days, is beyond normal day-to-day variations, is acute in onset, and may warrant a change in regular medication. The severity of COPD exacerbations is classified as follows:

- Mild: Exacerbations that do not require systemic steroids or antibiotics and do not result in hospitalisation or death.
- Moderate: Exacerbations that require treatment with systemic steroids and/or antibiotics, and do not result in hospitalisation or death.
- Severe: Exacerbations that result in hospitalisation or death.

All COPD exacerbations will be captured using a COPD exacerbation eCRF and will not be reported as AEs unless considered an SAE

3.5.4 Laboratory variables

Laboratory parameters will be recorded at Visit 1, pre-dose at visits 3, 6, 9, and at 24h post-dose at visits 5, 8, 11, and at follow-up. Safety laboratory tests will be done after 8 hours of fasting. Serology parameters will be measured at Visit 1 only.

The laboratory variables detailed in Table 2 will be recorded. In addition, urine pregnancy tests will be performed for women of childbearing potential. Additional safety samples may be collected if clinically indicated at the discretion of the Investigator. This last values will not be transferred to the Sponsor, if there are relevant abnormalities it will be reported as TEAE. Laboratory values of the form of “< x” (ie, below the lower limit of quantification) or > x (ie, above the upper limit of quantification) will be imputed as “x” in the calculation of summary statistics, but the original value (ie, “< x” or “> x”) will be displayed in the listings.

Table 2 Laboratory safety variables

Haematology/Haemostasis (whole blood)	Clinical Chemistry (serum or plasma)
B-Haematocrit	S/P-Glucose (fasting)
B-Haemoglobin	S/P-Cholesterol, total
B-Erythrocytes (red blood cells)	S/P-Triglycerides
B-MCV	S/P-Creatinine
B-MCH	S/P-Bilirubin, total
B-MCHC	S/P-Protein, total
B-Leukocyte count (white blood cells)	S/P-Albumin
B- differential blood count (neutrophils, lymphocytes, monocytes, eosinophils and basophil)	S/P-Uric acid and BUN
B-thrombocytes	S/P-Sodium
B-Platelet	S/P-Potassium
aPTT	S/P-Calcium, total
INR	S/P-Chloride
PTT	Alpha-1 antitrypsin
Urinalysis (dipstick)	S/P-Phosphorus, inorganic
U-pH	S/P-AST
U-Blood	S/P-ALT
U-leucocytes	S/P-ALP
U-Protein	S/P-GGT
U-Glucose	S/P-LDH
U-Bilirubin	S/P-Creatine kinase
U-Urobilinogen	S/P-Bicarbonate
U-Ketones	S/P-Magnesium
U-Nitrites	

ALP=Alkaline phosphatase; ALT=Alanine transaminase; aPTT=Activate partial thromboplastin time; AST=Aspartate transaminase; BUN=Blood urea nitrogen; GGT=Gamma glutamyl transferase; INR=International normalised ratio; LDH=Lactate dehydrogenase; MCH=Mean cell haemoglobin; MCHC=Mean corpuscular haemoglobin concentration; MCV=Mean corpuscular volume; PT=Prothrombin time; PTT=Partial thromboplasma time.

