8.2.1 Clinical safety laboratory assessments

See [Table 8](#) for the list of clinical safety laboratory tests to be performed and to the SoA ([Table 1](#)) for the timing and frequency. All protocol-required laboratory assessments, as defined in the table, must be conducted in accordance with the laboratory manual and the SoA. The results of tests performed at Screening (Visit 1 or Visit 2) will be regarded as baseline data.

The Investigator should make an assessment of the available results with regard to clinically relevant abnormalities. The laboratory results should be signed and dated and retained at centre as source data for laboratory variables.

For information on how AEs based on laboratory tests should be recorded and reported, see Section [8.3.7](#). Additional safety samples may be collected if clinically indicated at the

discretion of the Investigator. The date, time of collection and results (values, units and reference ranges) will be recorded on the appropriate eCRF.

The clinical chemistry, haematology and urinalysis will be performed at a central laboratory. The central laboratory will provide the centre with the necessary material and instructions for the sampling. In exceptional circumstances and upon discussion with the Sponsor, local laboratory assessments may have to be undertaken to collect key information supporting an AE or SAE. Information will be collected in eCRF as appropriate.

Table 8 Laboratory safety variables

Haematology/Haemostasis (whole blood)	Clinical Chemistry (serum or plasma)
B-Haematocrit	S/P-Glucose (fasting)
B-Haemoglobin	S/P-Cholesterol, total
B-Erythrocytes (red blood cells)	S/P-Triglycerides
B-MCV	S/P-Creatinine
B-MCH	S/P-Bilirubin, total
B-MCHC	S/P-Protein, total
B-Leukocyte count (white blood cells)	S/P-Albumin
B-differential blood count (neutrophils, lymphocytes, monocytes, eosinophils and basophil)	S/P-Uric acid and BUN
B-thrombocytes	S/P-Sodium
B-Platelet	S/P-Potassium
aPTT	S/P-Calcium, total
INR	S/P-Chloride
PTT	Alpha-1 antitrypsin
Urinalysis (standard dipstick as a minimum)	S/P-Phosphorus, inorganic
U-pH	S/P-AST
U-Blood	S/P-ALT
U-leucocytes	S/P-ALP
U-Protein	S/P-GGT
U-Glucose	S/P-LDH
U-Bilirubin	S/P-Creatine kinase
U-Urobilinogen	S/P- Bicarbonate
U-Ketones	S/P- Magnesium
U-Nitrites	

ALP=Alkaline phosphatase; ALT=Alanine transaminase; AST=Aspartate transaminase; BUN=Blood urea nitrogen; GGT=Gamma glutamyl transferase; LDH=Lactate dehydrogenase; MCH=Mean cell haemoglobin; MCHC=Mean corpuscular

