Appendix D Actions Required in Cases of Increases in Liver Biochemistry and Evaluation of Hy's Law

1 INTRODUCTION

This Appendix describes the process to be followed in order to identify and appropriately report Potential Hy's Law (PHL) cases and Hy's Law (HL) cases. It is not intended to be a comprehensive guide to the management of elevated liver biochemistries.

During the course of the study the Investigator will remain vigilant for increases in liver biochemistry. The Investigator is responsible for determining whether a subject meets potential PHL criteria at any point during the study.

All sources of laboratory data are appropriate for the determination of PHL and HL events; this includes samples taken at scheduled study visits and other visits including central and all local laboratory evaluations even if collected outside of the study visits; for example, PHL criteria could be met by an elevated ALT from a central laboratory **and/or** elevated TBL from a local laboratory.

The Investigator will also review Adverse Event data (for example, for AEs that may indicate elevations in liver biochemistry) for possible PHL events.

The Investigator participates, together with AstraZeneca clinical project representatives, in review and assessment of cases meeting PHL criteria to agree whether Hy's Law (HL) criteria are met. HL criteria are met if there is no alternative explanation for the elevations in liver biochemistry other than Drug Induced Liver Injury (DILI) caused by the Investigational Medicinal Product (IMP).

The Investigator is responsible for recording data pertaining to PHL/HL cases and for reporting Serious Adverse Events (SAEs) and Adverse Events (AEs) according to the outcome of the review and assessment in line with standard safety reporting processes.

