3 IDENTIFICATION OF POTENTIAL HY'S LAW CASES

In order to identify cases of PHL it is important to perform a comprehensive review of laboratory data for any subject who meets any of the following identification criteria in isolation or in combination:

$$\text{ALT} \geq 3\text{xULN}$$

$$\text{AST} \geq 3\text{xULN}$$

$$\text{TBL} \geq 2\text{xULN}$$

When a subject meets any of the PHL identification criteria, in isolation or in combination, the central laboratory will immediately send an alert to the Investigator (also sent to AstraZeneca representative).

The Investigator will also remain vigilant for any local laboratory reports where the PHL identification criteria are met, where this is the case the Investigator will:

- Notify the AstraZeneca representative
- Request a repeat of the test (new blood draw) by the central laboratory without delay
- Complete the appropriate unscheduled laboratory CRF module(s) with the original local laboratory test result

When the identification criteria are met from central or local laboratory results the Investigator will without delay:

- Determine whether the subject meets PHL criteria (see Section 2 within this Appendix for definition) by reviewing laboratory reports from all previous visits (including both central and local laboratory results)

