3.1.2 Repeated and unscheduled visits

All repeated and unscheduled measurements will be presented in the listings. Repeated and unscheduled measurements will not be used for statistical analysis or summary tables, unless the repeated measurement was performed due to unreliable values/technical reasons, or the repeated measurement occurred prior to IP administration and is defined as the 'baseline'. The following general rules will apply to all repeated and unscheduled measurements (the below section describes a different approach for spirometry variables):

- For repeated measurements obtained prior to the first dose of IP in each period, the latest reliable value (which may be scheduled or unscheduled) will be used in the calculation of descriptive statistics
- For repeated measurements obtained at the designated Baseline visit, the latest reliable value (which may be scheduled or unscheduled) will be defined as the Baseline in each period. Repeated measurements designated Baseline will be used in descriptive statistics rather than the planned measurement they replace
- For repeated measurements obtained at any time point after the first dose of IP, the first reliable value of any repeated measurements will be used in the calculation of changes from Baseline and for the descriptive statistics.

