
Category 1: QTcF value above the following cut-off at any time during treatment
 
Criteria:
 
 >450 (ms) >480 (ms) >500 (ms) 
Category 2: QTcF increase by more than following cut-off at any time during treatment
 
Criteria:
 
 >30 (ms) >60 (ms) >90 (ms) 
Category 3: QTcF value above cut-off and QTcF increase by more than cut-off at any time during treatment
 
Criteria:
 
 Value >450(ms) and Increase >30(ms) Value >500(ms) and Increase >60(ms)
--

Table 5 PCS ECG criteria: Heart Rate and QRS interval

ECG parameter	Category	Criterion 1	Criterion 2
Heart rate	Tachycardia event	≥ 110 bpm and an increase of $\geq 15\%$ over baseline value	≥ 120 bpm if baseline is < 100 bpm
	Bradycardia event	≤ 50 bpm and a decrease of $\geq 15\%$ over baseline value	≤ 40 bpm if baseline is > 40 bpm
QRS interval		≥ 100 msec and an increase of $\geq 25\%$ over baseline value	≥ 150 msec if baseline is < 150 msec
PR interval		≥ 200 msec and an increase of $\geq 25\%$ over baseline value	≥ 250 msec if baseline is < 250 msec

bpm = beats per minute.

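### SAP 3.5.4 says extra laboratory results will not reach the sponsor, which contradicts the protocol, and SAP 3.1.2 leaves clinically triggered ECGs out of QTcF counts defined over the whole of treatment

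*SAP*

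**What the plan says.** **Extra laboratory samples.** SAP 3.5.4 allows additional safety samples when clinically indicated and then states: "This last values will not be transferred to the Sponsor, if there are relevant abnormalities it will be reported as TEAE". Protocol 8.2.1, on the same samples, says: "The date, time of collection and results (values, units and reference ranges) will be recorded on the appropriate eCRF". Protocol Appendix D, section 1, says: "All sources of laboratory data are appropriate for the determination of PHL and HL events", and spells out that this covers local results and results obtained outside study visits. Appendix D, section 3, instructs the investigator, for a local result that meets a liver criterion: "Complete the appropriate unscheduled laboratory CRF module(s) with the original local laboratory test result". SAP 4.4.1.2 plans to list all laboratory data held in the eCRF, and to list patients whose ALT or AST and total bilirubin are raised at any time.

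**Unscheduled measurements in general.** SAP 3.1.2 puts all of them in the listings. For tables it says: "Repeated and unscheduled measurements will not be used for statistical analysis or summary tables, unless the repeated measurement was performed due to unreliable values/technical reasons". The second exception applies where a pre-dose repeat becomes the baseline ("or the repeated measurement occurred prior to IP administration and is defined as the" baseline). After the first dose, the first reliable value among repeats is used.

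**QTcF outliers.** Category 1 of SAP Table 4 reads: "QTcF value above the following cut-off at any time during treatment". Categories 2 and 3 carry the same time span. SAP 4.4.1.3 presents these categories, and the Table 5 potentially clinically significant (PCS) ECG values, as numbers and percentages of patients, both overall and by timepoint.

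**The concern.** Unscheduled tests are usually done because a patient has symptoms or a value looks worrying, so they are the measurements most likely to hold an extreme. Protocol 2.3 names cardiac effects among the relevant potential risks. A data manager cannot obey both SAP 3.5.4 and Protocol 8.2.1, and a programmer cannot apply SAP 3.1.2 and also produce a QTcF count that covers all of treatment. At stake are whether safety data that the protocol requires arrive in the database, and whether the QTcF outlier table reports what its definition says.

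**Working it through.** The point concerns data-handling rules, and the plan gives no figure to reproduce. The check sets the rules side by side for each output and then counts the scheduled assessments.

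**1. Hy's Law listing (SAP 4.4.1.2).**
- The output is a listing. SAP 3.1.2 restricts analyses and summary tables but sends every unscheduled value to the listings, so it removes nothing here.
- The only threat is the SAP 3.5.4 sentence: values that are not transferred cannot be listed.
- That sentence conflicts with Protocol 8.2.1, Appendix D sections 1 and 3, and SAP 3.1.2. SAP section 6, which records changes from the protocol, does not mention it.
- Reporting the abnormality as a TEAE does not supply the value. The AE variables in Protocol 8.3.4 include no laboratory result. Protocol 8.3.7 makes deterioration in a protocol-mandated test an AE only if it meets SAE criteria or causes discontinuation; an accompanying symptom is reported in its own right.

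**2. QTcF category counts (SAP Table 4).**
- These are summary tables, so SAP 3.1.2 applies.
- An off-schedule post-dose ECG done for a clinical reason fits neither exception. It is not a technical repeat and not a pre-dose baseline.
- Protocol 8.2.4 allows extra ECGs when a result is clinically relevant or doubtful. Protocol 7.1 requires a repeat to confirm a QTcF withdrawal criterion (above 500 ms, or a change above 60 ms).
- Under the first-reliable-value rule, the reading that triggers a repeat is counted and the repeat is not. For example, a rise between 60 and 90 ms followed by a repeat above 90 ms is counted in the 60 ms category but not in the 90 ms one.

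**3. Scheduled assessments per treatment period** (SoA footnotes h, j and k; SAP 3.5.4 and 3.5.5).
- Post-dose ECGs: 4 from Day 1, 2 on Day 8 and 4 from Day 14, so 4 + 2 + 4 = 10. None falls on Days 3 to 7 or 9 to 13, which is 5 + 5 = 10 of the 14 dosing days.
- Post-dose central chemistry: 1, at 24 hours after the Day 14 dose. The next sample follows the 42 to 49 day wash-out or comes at follow-up.
- Post-dose i-STAT potassium and glucose: 4 from Day 1 and 4 from Day 14, so 4 + 4 = 8.

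**4. Size of one uncounted patient.** Taking the planned 72 randomised and 54 completing patients as bounds for the number contributing to a treatment, 1/72 = 1.4% and 1/54 = 1.9%.

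**The case against.** The strongest case on the other side has four parts.

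- **Liver signals reach the sponsor anyway.** Under Appendix D, a local result that meets a liver criterion leads to notification of the sponsor's representative, a central repeat and CRF entry. A full potential Hy's Law case is reported as an SAE within 1 day. This stands. It means the signal would not be lost, but it does not put the values into a listing that needs them.
- **The ECG values are not hidden.** SAP 3.1.2 and 4.4.1.3 list them all, a scheduled QTcF value that prompts a repeat is still counted, and QTcF above 500 ms is itself a withdrawal criterion once confirmed. This also stands, but a listing does not correct a count.
- **Table 4's specific wording might override the general rule in SAP 3.1.2.** That reading is possible, but SAP 3.1.2 names its exceptions and this is not one of them.
- **The stakes are modest.** Safety is largely descriptive, the study is exploratory, the primary efficacy analysis is untouched, and Protocol 2.3 reports no clinically significant ECG or laboratory abnormalities in humans to date. This stands.

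A reader might infer more than the documents support:
- that SAP 3.1.2 empties the Hy's Law listing. It does not, because it governs tables.
- that every summary table excludes all unscheduled values. Two exceptions are stated.
- that potassium extremes can be seen only in unscheduled tests. i-STAT potassium is scheduled around Days 1 and 14.

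**Conclusion.** The point holds, and both rules are wrong as written.

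First, SAP 3.5.4 contradicts the protocol and SAP 3.1.2 on whether additional laboratory values reach the sponsor, and the change is undeclared. The loss from the Hy's Law listing depends on that sentence being followed. It is an unresolved contradiction, not a certain omission.

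Second, applying SAP 3.1.2 literally makes the Table 4 counts incomplete against their own definition, by off-schedule ECGs taken for clinical reasons and by repeats that cross a higher cut-off.

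Each uncounted patient is worth 1.4 to 1.9 percentage points, assuming 54 to 72 patients per treatment. The documents give no basis for predicting how many there would be. The effect is on the completeness of safety reporting only.

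**What to change.** 1. In SAP 3.5.4, delete or correct the non-transfer sentence. Additional and local laboratory results entered in the eCRF should be transferred and used in the Hy's Law listing, in line with Protocol 8.2.1 and Appendix D.
2. In SAP 3.1.2, add one exception. For the overall post-baseline counts of QTcF categories (Table 4) and PCS ECG values (Table 5), a patient is counted if any reliable post-baseline value in the period, scheduled or unscheduled, meets the criterion. By-timepoint summaries and model analyses stay on scheduled values.

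An any-value rule is preferable to a single worst value, which is undefined for heart rate because Table 5 has both high and low limits. The exception should not extend to vital signs: SAP 4.4.1.4 counts those by day and timepoint only and produces no overall count.

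The cost is SAP wording and one derived flag. No new data are collected, because the protocol already requires the laboratory results in the eCRF and the SAP already lists all ECGs.

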3.5.5 ECG

Electrocardiogram will be performed during Screening Visit, and then at pre-dose and 1, 2, 4, and 24 hours post-dose on Visits 3, 5, 6, 8, 9 and 11. At Visits 4, 7 and 10 measurements will be done at 1 and 4 hours post-dose. ECG will also be performed at follow-up. ECG should be performed before spirometry.

Number of ECG abnormalities in each category of conduction defects, rhythm, myocardial infarction and others will be reported at each timepoint from each day within each treatment.

The following ECG parameters will be analyzed:

- Heart rate (except pre-dose on Visits 4, 7 and 10, which will be taken from vital signs).
- RR interval: Duration in milliseconds between two R peaks of two consecutive measurements
- QRS complexes
- PR interval: Duration in milliseconds from the beginning of wave P to onset of ventricular depolarisation (Q and R)
- QRS interval: Duration in milliseconds of the QRS complex
- QT interval: Duration in milliseconds from the beginning of Q wave to the end of the T wave
- QTc interval: QT interval corrected by heart rate:
 - QTcF interval: QT interval corrected using Fridericia's formula
($QT[\text{msec}]/RR[\text{sec}]^{1/3}$)
- Sinus rhythm
- Overall evaluation (normal/abnormal)

For HR, and QTcF parameters, between-group differences will be presented at each timepoint (day, timepoint (hours) within day).

3.5.6 Vital signs

Systolic and diastolic blood pressure (BP) will be recorded at screening, pre-dose and 1, 2, 4, and 24 hours post-dose at Visits 3, 5, 6, 8, 9 and 11. On Visits 4, 7 and 10 blood pressure will be measured at pre-dose, 1 and 4 hours post-dose. BP will also be recorded at follow-up. Body temperature will be measured at Screening and at the Follow-up Visit. Heart rate will be assessed by ECG (except pre-dose on Visits 4, 7 and 10, which will be taken from vital signs).

CCI

4. ANALYSIS METHODS

4.1 General principles

4.1.1 Statistical testing

This study is exploratory in nature. The main comparisons of interest are

- AZD8871 600 µg versus Anoro® Ellipta® and
- AZD8871 600 µg versus Placebo.

No adjustment of the Type I error for multiple comparisons will be made in the study, as the primary purpose is estimation rather than hypothesis testing.

4.1.2 Presentation of results

All analyses will use SAS® version 9.3 or higher. Unless otherwise specified, summary tables will be presented by treatment group, labelled as follows: AZD8871 600 µg, Anoro® Ellipta®, and Placebo.

All data will be presented in listings, sorted by sequence, patient number, and treatment. Continuous variables will be summarised by the number of observations, mean, standard deviation (SD), median, minimum, and maximum. Categorical variables will be summarized by frequency counts and percentages for each category. Unless otherwise stated, percentages will be calculated out of the population total for the corresponding treatment.

The minimum and maximum will be reported to the same number of decimal places as the raw data recorded in the database. The mean, median and standard deviation will be reported to one more decimal place than the raw data recorded in the database. The maximum number of decimal places presented for any statistic shall be four, except for pulmonary function variables, where the maximum shall be three. Decimals to be used for PK analysis is described in section 4.3.

Percentages will be presented to one decimal place.

All confidence intervals (CIs) will be two-sided 95% CIs, unless stated otherwise, and presented to one more decimal place than the raw data recorded in the database. If a model is used to estimate the treatment difference, the corresponding CI according to the model will be presented. Otherwise, the unadjusted CI will be used. Nominal p-values may also be presented. Care should be taken when interpreting CIs and p-values since no correction for

multiple testing is done for the endpoints. The presentation of p-values- will be to four decimal places unless a p-value is less than 0.0001, in which case “<0.0001” will be displayed.

A month and a year are operationally defined to be 30.4 and 365.25 days respectively.

